### **ASSESSMENT OF EFFICACY**

### **Primary Efficacy Endpoint:**

Percentage in each group with SUA levels <360µmol/L (the saturation point form sodium urate crystal formation).

### **Secondary Efficacy Endpoints:**

Percentage in each group with reduced number of acute attacks in the second year of the study

Quality of life scores (SF36 and GAQ) at end point compared to baseline in each group and comparison of endpoint QOL scores between the two groups.

Reduction in size and number of tophi.

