	individualised lifestyle modification advice and ULT to reduce SUA to below the saturation point for sodium urate crystal formation (360 µmol/L). Individuals in this group will be followed up regularly according to their clinical need/monitoring requirements.  Standard care/control participants will have a single nurse contact at baseline during which they will be provided with the Arthritis Research UK leaflet on gout and be informed on appropriate management of acute attacks. There will be no discussion on other aspects of gout management – if asked about lifestyle and ULT participants will be asked to question their GP about this. This group will be asked to provide a blood sample at 0, 12 and 24 months and also keep a diary of acute attacks over the next 2 years and complete a questionnaire (including QOL assessment) at 12 and 24 months.
Duration of study  Randomisation and blinding	Total – 3 years Per participant – 2 years Planned recruitment start date 1 January 2013 Study participants in the RCT will be aware that they have been randomised to either a nurse-led intervention or to continue standard care/GP-led management.
	Randomisation will be undertaken by the CTU using a web based, computer generated, stratified (by GP practice) random block system and undertaken by the CTU. Following randomisation participants and nurses will obviously both know which group they are in. Although participants will be aware that the study objective is to compare cost effectiveness of nurse versus doctor led management of gout they will not be informed prior to randomisation concerning the recommended best practice strategies which include ULT and treating to target.
Outcome measures	Primary outcome – SUA of <360 µmol/L at study end Secondary outcomes – reduction in number of self-reported acute attacks in year two; improved QOL scores (SF36, Gout Assessment Questionnaire - GAQ); reduction in tophus size and number; cost effectiveness and cost utility based on health utilisation cost and SF6D (derived from SF36).

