### **Secondary endpoints:**

Percentage with reduction of frequency of acute attacks in the second year. Difference in QOL scores for SF36 and GAQ at end of study.

Percentage with reduction in size of the largest index tophus and reduction in number of tophi.

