### Inclusion criteria:

- All Adults aged 21 and over with a GP given diagnosis of gout, confirmed following telephone interview to ensure that participants fulfil ACR criteria for gout.
- Nurse intervention and standard care groups (RCT) at least one acute attack of gout in the previous year.

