### Power calculations:

Information that includes SUA on community-derived patients with gout is sparse. However, detailed information on frequency of attacks, treatment, SUA and quality of life is available for 250 gout patients from 17 practices in Nottingham (5, 11). In this survey: 30% of patients were on ULT; the rate for acute attacks in the previous year was 32% for patients on ULT and 57% for patients on no ULT; mean SUA was 318  $\mu$ mol/L in those taking ULT compared to 434  $\mu$ mol/L in those not taking ULT; and 23% of those taking ULT had a SUA >360  $\mu$ mol/L, compared to 75% of those not on ULT. For quality of life (SF36) overall mean and SD for those on ULT was 16.41 (2.81) compared to 15.67 (3.05) for those not on ULT, giving a pooled SD of 3.09 and a mean difference of 0.7 between groups (the latter is used as a proxy of effect size d).

According to these results, we have estimated the following sample size requirements, to achieve 90% power at 0.05% significance level, for each outcome:

- reduction in frequency of acute attacks in final year a sample size of 90 is required for each arm
  - reduction in SUA below the therapeutic target a sample size of 70 patients is required for each arm
- quality of life a sample size of 233 is required for each arm (80% power at 0.05% significance level

Allowing a 10% drop-out rate over the 2 years, this requires a total of **512 patients** (233 plus 23 dropouts in each arm) to provide adequate power for the primary outcome and for 2 of the key secondary outcomes. There are no data on changes in GAQ in response to treatment, but being a disease-specific instrument, we assume that the GAQ will be more sensitive to change than the SF36 and that a total size of 796 will be adequately powered for this outcome.

The total number of GP practices in Nottinghamshire is 170 and the estimated number of registered patients with gout is 10,720 (i.e. an average of 65 patients per GP). A questionnaire will be sent to all patients (unless they have an exclusion criterion) to detect eligible patents. A random sample of those eligible will be selected using the simple random selection after the consent to the trial.

Page **20** of **29** Final version 8 –18 May 2015

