# A community based randomised controlled trial comparing nurse-led intervention with standard care

# -Analysis plan

Synopsis of the design: A 2 year community based randomised controlled trial will be undertaken in Nottingham to investigate clinical effectiveness and cost-effectiveness of a nurse-led quality of care intervention versus standard of care control. A questionnaire survey will be undertaken in the GP practices in Nottinghamshire to obtain 724 patients with gout according to the American College of Rheumatology (ACR) criteria and at least one acute attack in the past year. They will be randomly allocated to the intervention and the control group using stratified (according to the participated GP practices), block (fixed block of 4 for random allocation to keep the balance between the groups) randomisation method. Participants will be examined at baseline, 12 months and 24 months for outcomes such as serum uric acid (SUA), number of acute attacks in the previous year and quality of life (QoL) (SF36).

Principles of analysis: Intention to treat (ITT) analysis will be conducted. Descriptive analysis on raw differences between groups at baseline, 12 months and 24 months will be undertaken. Multi-level regression model (MLM) will be used for the overall comparison of the treatment effect between groups with repeated measures and missing data. We shall include all data from 3 time points in the same model, with repeated measures as level 1 units and individuals as level 2 units. The treatment group and time points will be considered as covariates in the model together with covariates at baseline for the adjustment purpose. Continuous data (eg, SUA, QoL score, etc) will be analysed using MLM linear regression, whereas dichotomous and categorical data will be analysed using MLM logistic or multinomial models. Comparison will be made between the intervention and the control in the RCT, as well as between the control in the RCT and the observational group.

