# 2. Secondary outcomes

- Number of acute attacks in preceding year, year 1 and year 2 within each group and between groups
- Number of patients with tophi at baseline, 12 months and 24 months with each group and between groups
- Mean QoL scores (overall, different domain scores of SF36 and the Gout
   Asssessment Questionnaire (GAQ) including the Gout Impact Scale (GIS) of the GAQ.
   at 0, 12 and 24 months within each group and between groups
- Mean change of QoL scores from baseline to 12 months and 24 months within each group and between groups

**Covariates and baseline predictors:** age, gender, body mass index, disease duration, tophi, associated comorbidity etc.

Task allocation and timetable: The Nottingham CTU will undertake randomisation, development of the database for RCT and the web-based data entry platform. CTU will also conduct data monitoring and quality control for the RCT data. Academic Rheumatology will recruit patients, enter the data through a web-based data entry platform for the RCT data and develop an independent database for the observational group. Both datasets are not open for any interim analysis between baseline and 24 months to keep the randomisation. Analysis will start after 24 months when the data has been fully completed, quality checked over and closed. Analysis for clinical effectiveness (efficacy and side effects) will be completed in 3 months after the closing date of the data. Analysis for cost-effectiveness will be completed in 12 months, as it requires acquisition of additional data for cost. In brief:

- Recruitment 8 months
- RCT and observation 24 months
- Results for clinical effectiveness 3 months
- Results for cost-effectiveness 12 months

Economic Analyses Plan.

Two economic analyses are planned: the first being an economic analysis alongside the RCT and the second modelling the costs and benefits over a longer time horizon. The base case in both models would use an NHS perspective, with a societal perspective (that include indirect costs such as lost productivity) being undertaken in a sensitivity analysis.

Economic analysis alongside the RCT

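### The attack outcome is a percentage 'reduced' with no reference year in the protocol and an unmodelled count in the analysis plan, and its stated power belongs to a third quantity

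*Supplement*

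**What the plan says.** **Endpoint in the protocol (version 8, 18 May 2015).** The list under Secondary endpoints gives "Percentage with reduction of frequency of acute attacks in the second year". The section Assessment of efficacy gives "Percentage in each group with reduced number of acute attacks in the second year of the study". Both are yes/no outcomes per patient, and neither names the period against which a reduction is judged. The Synopsis is looser: "reduction in number of self-reported acute attacks in year two".

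**Endpoint in the analysis plan (17 July 2013).** Under Secondary outcomes it lists "Number of acute attacks in preceding year, year 1 and year 2 within each group and between groups", which is a count.

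**Population.** The inclusion criteria require "at least one acute attack of gout in the previous year".

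**Models.** The protocol's statistical methods name chi-square for categorical and ANOVA for continuous data. The analysis plan assigns continuous data to multilevel linear regression, "whereas dichotomous and categorical data will be analysed using MLM logistic or multinomial models". Neither document names a count model or says which of these models the attack count goes into.

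**Power.** Power calculations quotes a survey in which "the rate for acute attacks in the previous year was 32% for patients on ULT and 57% for patients on no ULT", and concludes: "reduction in frequency of acute attacks in final year a sample size of 90 is required for each arm". The Synopsis repeats the 90 at 90% power and a two-sided 5% level.

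**The concern.** Reduced attack frequency is one of the two key secondary outcomes for which the protocol claims adequate power. Four things are unsettled.

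- The two documents define different endpoints, so which one is reported could be decided after the data are seen.
- The reference year is open. Against year 1, a patient with no attacks in year 1 can never be reduced. Against the year before entry, a recalled count is compared with a diary count.
- Everyone enters with at least one attack. Many will have fewer later without any treatment effect, and a fall from 5 to 4 scores the same as a fall from 5 to 0.
- The stated power refers to none of the written endpoints.

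**Working it through.** **1. Reproduce the 90 per arm.** Inputs from Power calculations and the Synopsis: 57% v 32%, 90% power, two-sided 5%.

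n = [1.960·√(2·p̄·q̄) + 1.2816·√(p₁q₁ + p₂q₂)]² / (p₁ − p₂)², with p̄ = 0.445.

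- √(2 × 0.445 × 0.555) = 0.703 and √(0.2451 + 0.2176) = 0.680.
- n = (1.378 + 0.872)² / 0.0625 = 80.9, so 81 per arm.
- With continuity correction: (80.9/4) × [1 + √(1 + 4/(80.9 × 0.25))]² = 88.8, so 89 per arm.

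The 90 therefore reproduces, but as the sample size for *any attack in a year*, comparing ULT users with non-users in a survey with no stated recent-attack criterion. The 0.05% level printed in Power calculations would need 177–185 per arm, so 5% was used. At 57% v 32% the power is 92.8% with 90 per arm and 99.98% with 233.

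**2. Translate the planning contrast into a rate ratio.** Under a simple Poisson model, ln(1 − 0.32)/ln(1 − 0.57) = 0.386/0.844 = 0.46.

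**3. What selection does.** The documents give no distribution of attack counts, so what follows rests on assumptions. Counts in the baseline year and in year 2 are Poisson with a gamma-distributed patient rate: population mean 0.8–2.5 a year, frailty variance 0.5–2, year-to-year frailty correlation 0.5–1.0. Patients are kept if the baseline count is at least 1, and a reduction is judged against that baseline year.

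- With no treatment effect, about 47–64% of controls are reduced.
- About 53–86% of controls still have an attack in year 2; the power calculation used 57%.
- Example (mean 1.5, variance 1, correlation 0.8): the mean count falls from 2.49 at baseline to 1.99 in year 2 untreated, and 54.6% are reduced.

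**4. Cost in power, 233 per arm.** Chi-square on reduced against negative binomial regression adjusted for log baseline count, 400 runs per scenario (standard error up to 2.5 points):

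| True rate ratio | Percentage reduced | Baseline-adjusted count | Scenarios |
|---|---|---|---|
| 0.8 | 23–58% | 42–87% | full grid |
| 0.7 | 50–93% | 79–100% | full grid |
| 0.56 | 88–99% | 99–100% | variance 1, correlation 0.5 and 0.8 |
| 0.4 | 99–100% | 100% | variance 1, correlation 0.5 and 0.8 |

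Hand check of one cell (mean 1.5, variance 1, correlation 0.8, rate ratio 0.8): 54.8% v 61.9% reduced. The standard error is √(2 × 0.5835 × 0.4165/233) = 0.0457, so z = 0.071/0.0457 = 1.55, and power is Φ(1.55 − 1.96) = 34%. The simulation gave 35%, against 64% for the adjusted count.

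**5. Where the gain comes from.** In further runs at 233 per arm and rate ratio 0.8, percentage reduced had 37–50% power, the baseline-adjusted count model 62–81%, and a baseline-adjusted linear model 61–82%. Keeping the count and adjusting for its baseline matters more than the choice of error distribution.

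**The case against.** **The count is already planned.** The analysis plan lists the number of attacks between groups and puts baseline covariates in a multilevel model. This stands. A reader might infer that the trial analyses attacks only as a percentage and so loses power, but the documents do not support that. If the count went into the plan's linear model with baseline adjustment, little would be lost. What remains is that the protocol says something else and that no text assigns the count to a model.

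**The loss depends on the effect.** This stands too. Near the planning contrast (rate ratio about 0.46) both analyses have ample power at 233 per arm. The planning contrast, however, compares ULT users with non-users, not nurse-led with usual care. If 30% of controls took ULT, as in the survey, the control proportion would be 0.3 × 32% + 0.7 × 57% = 49.5%. The implied rate ratio is then ln(0.68)/ln(0.505) = 0.56, still an effect at which percentage reduced has 88–99% power in the scenarios run.

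**The 90 has no effect on trial size.** Correct: quality of life sets 233 evaluable per arm. Even 49.5% v 32% would need only 164 per arm. The 90 is a labelling fault and does not show that the trial is too small.

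**Regression to the mean acts in both arms.** Correct. A reader might take the high untreated rate as bias. Under randomisation it is not; it dilutes the contrast and makes the percentage hard to interpret.

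**Conclusion.** The point holds as a fault of specification with a measurable cost in efficiency. The protocol and the analysis plan define different attack endpoints, the protocol's has no reference year, the plan's has no assigned model, and the quoted 90 per arm is the power of neither.

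The size of the loss rests on assumed gamma-Poisson counts, because the documents give none, and the ranges are wide for that reason. In the scenarios run it is substantial at rate ratios of 0.7–0.8 and small or absent at about 0.5 or below. The primary outcome and the total sample size are unaffected. This should be changed, but it does not threaten the trial's main conclusion.

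**What to change.** 1. In both documents, make the between-group endpoint the number of diary-recorded attacks in year 2.
2. Analyse it by negative binomial regression (or Poisson with robust standard errors), with log observed time in year 2 as offset and the attack count in the year before entry as covariate. If practice is included, enter it as a random effect. Report the rate ratio with a 95% confidence interval.
3. Keep percentage reduced as a descriptive summary with its reference year stated. Note that the pre-entry count is recalled while year 2 comes from a diary.
4. In the Synopsis and Power calculations, say that the 90 per arm refers to the proportion with any attack in the survey, or drop it as the stated power for this outcome.

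The cost is wording: the diary and the baseline attack history are already collected. The one small downside is that a rate ratio is less familiar to readers than a percentage; the descriptive summary in item 3 offsets this.

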### TRIAL / STUDY OBJECTIVES AND PURPOSE

### **PRIMARY OBJECTIVE:**

To determine in community-based patients with untreated or under treated gout the effectiveness and cost effectiveness of a nurse-led complex intervention compared to standard GP led care.

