### **STATISTICS**

### Methods

The trial statistician ([name]) will oversee the data management, evaluation and analyses. The database will be developed in collaboration with the CTU using access and analysed using SPSS. SUA will be analysed at baseline, 12 months and 24 months. Comparison will be undertaken between the nurse led intervention and control at each observational point. There will be no interim analyses for efficacy or safety. Intention to

Page **19** of **29** Final version 8 –18 May 2015

treat (ITT) analysis will be undertaken to compare treatment effects between groups. Multilevel models will be used for any missing outcome measures. Chi-square test will be used for dichotomous or categorical data and ANOVA test will be used for continuous variables. Adjustment will be made for baseline co-variables as appropriate. Cost per QALY will be estimated from the SF6D and the direct and indirect costs related to gout and its management.

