# **Outcome measures:**

- 1. Primary outcome: % patients hitting the therapeutic target (SUA≤ 360 μmmol/l) is the primary outcome of the trial. We will examine
  - % patients reaching the target at baseline, 12 months and 24 months within each group
  - % patients reaching the target at baseline, 12 months and 24 months between groups
  - Mean SUA at baseline, 12 months and 24 months within each group
  - Mean SUA at baseline, 12 months and 24 months between groups
  - Mean change of SUA from baseline to 12 months and 24 months within each group
  - Mean change of SUA from baseline to 12 months and 24 months between groups We will also calculate the number needed to treat (NNT) for % patients reaching the therapeutic target SUA less than 360  $\mu$ mol/l, as appropriate.

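### Quality of life against baseline within each arm is listed as an efficacy endpoint, and other within-group comparisons carry no descriptive label; minor, because the between-group comparisons are also planned and are unaffected

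*Supplement*

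**What the plan says.** The primary objective in protocol version 8 is the "effectiveness and cost effectiveness of a nurse-led complex intervention compared to standard GP led care".

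Under Assessment of Efficacy, Secondary Efficacy Endpoints, the quality-of-life endpoint has two parts. The first is "Quality of life scores (SF36 and GAQ) at end point compared to baseline in each group". The same sentence goes on: "and comparison of endpoint QOL scores between the two groups".

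The analysis plan (July 2013) follows the same pattern. For the primary outcome it lists the percentage of "patients reaching the target at baseline, 12 months and 24 months within each group", then the between-group version, and does the same for mean uric acid and its change. Its secondary outcomes include "Number of acute attacks in preceding year, year 1 and year 2 within each group and between groups", with similar lines for tophi, quality-of-life scores and their change.

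Elsewhere the comparison is between groups. The design section gives the quality-of-life endpoint as "Difference in QOL scores for SF36 and GAQ at end of study". Statistics, Methods says "Comparison will be undertaken between the nurse led intervention and control at each observational point". The analysis plan's principles assign a multilevel model to the overall comparison of treatment effect between groups. The one sentence there that uses the word descriptive concerns raw differences between groups, not change within a group.

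The inclusion criteria require "at least one acute attack of gout in the previous year".

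**The concern.** The null hypothesis of a within-arm comparison with baseline is that nothing changes over time in that arm. It can be false when nurse-led and GP-led care are equally effective. Patients enter because they had an attack in the past year, so their prior-year count is selected to be high and should fall on average afterwards in both arms.

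If such a comparison stands as an efficacy endpoint, an improvement in the nurse arm could be reported as meeting it even where the randomised difference is null. The plan has no rule for that disagreement. It also leaves room for reading significance in one arm but not the other as evidence of benefit. The background section says that what is missing for a policy submission is evidence that quality of life improves because of successful management. Only the randomised contrast can supply that.

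**Working it through.** The plan states no figure on this point, so there is none to reproduce. The check asks how often a within-arm test would be significant if the intervention had no effect. The plan names no within-arm test; a two-sided paired t-test at 5% is assumed for illustration.

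**Inputs from the protocol (Power calculations)**
- 30% of surveyed patients on urate-lowering therapy, with an attack rate of 32% in the previous year; 57% in those not on it.
- 233 patients per arm after dropout.
- SF36 SD 3.09 and difference 0.7.

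**Inputs assumed (not in the documents)**
- Stable patient-level attack rates, either all equal (Poisson) or varying as a gamma distribution with shape k (smaller k means more spread).
- Quality-of-life correlation r between baseline and 24 months of 0.3 to 0.7.
- A common quality-of-life drift of up to 0.7 points.

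**Attacks**

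Proportion with at least one attack in a year: 0.3 × 0.32 + 0.7 × 0.57 = 0.495, so P(no attack) = 0.505.

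The mean rate m is set to match this. Poisson: m = −ln(0.505) = 0.683. Gamma: m = k(0.505^(−1/k) − 1).

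Among patients who enter (at least one attack):
- mean in the prior year = m / 0.495;
- mean in year 2 with no effect = [m − 0.505 × m/(1 + m/k)] / 0.495, or simply m in the Poisson case.

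Example, k = 1: m = 0.980; prior year 0.980/0.495 = 1.98; year 2 = (0.980 − 0.505 × 0.980/1.980)/0.495 = 1.48.

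| Rates between patients | Mean, prior year | Mean, year 2, no effect | Significant fall within an arm |
|---|---|---|---|
| Poisson | 1.38 | 0.68 | 100% |
| k = 2 | 1.65 | 1.05 | 100% |
| k = 1 | 1.98 | 1.48 | over 99% |
| k = 0.5 | 2.95 | 2.57 | about 73% |
| k = 0.3 | 5.30 | 5.03 | about 28% |

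The last column is from simulation with 233 per arm and at least 2,000 trials per row. Repeated runs gave 72% to 74% at k = 0.5 and 26% to 28% at k = 0.3. In the same trials the between-arm t-test on year-2 counts rejected in about 4% to 6%.

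The chance that exactly one arm is significant is 2p(1 − p): 2 × 0.73 × 0.27 = 39% at k = 0.5, and 2 × 0.28 × 0.72 = 40% at k = 0.3.

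**Quality of life**

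SE of the mean change in one arm = 3.09 × √(2(1 − r)/233). At r = 0.5 this is 0.202. The chance of significance is P(|Z + drift/SE| > 1.96).

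| Common drift (SF36 points) | r = 0.3 | r = 0.5 | r = 0.7 |
|---|---|---|---|
| 0 | 5% | 5% | 5% |
| 0.2 | 13% | 17% | 25% |
| 0.35 | 31% | 41% | 61% |
| 0.7 | 83% | 93% | 99% |

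Simulation at r = 0.5 put the between-arm test of endpoint scores at 4.5% to 5.5% for drifts of 0, 0.35 and 0.7. A drift shared by both arms cancels in that comparison.

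**The case against.** The strongest reply is that the trial's question is answered elsewhere in the plan. The quality-of-life sentence itself continues to the between-group comparison. The design section, the statistical methods and the multilevel model all state the comparison as nurse-led against control, and each within-group line in the analysis plan has a between-group partner. All of this stands. A reader who stopped at the first clause might infer that within-arm comparison with baseline replaces the randomised contrast; the documents do not support that.

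It is also true that the plan speaks of comparing and examining, names no paired or other within-arm test, and nowhere says that significance will be contrasted across arms. Several within-group lines are most naturally read as summaries by arm and visit. The rejection rates above are therefore conditional on a test the plan does not name.

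The quality-of-life case is weaker than the attack case. Entry selects on an attack at any time in the past year, not on a low score, and SF36 during attacks is collected on separate forms. Drift in the scheduled scores is possible but not shown.

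What survives is narrower. One within-arm comparison is listed by name as an efficacy endpoint, the others are not marked descriptive, and no sentence says that effectiveness conclusions will not rest on them.

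**Conclusion.** The point holds as a minor one. Within-group comparisons with baseline cannot answer the nurse-versus-GP question, yet one stands among the efficacy endpoints and the rest are unlabelled. For attacks, a fall in both arms is expected from the entry rule; a paired test would find it in about 28% to 100% of trials with no effect, against about 5% for the between-arm test. The range depends on the assumed spread of attack rates, on stable patient-level rates and on a paired test being used. For quality of life the figures are illustrative only, since neither drift nor correlation is given in the documents.

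It should not be inferred that the between-group results are biased or that their type I error is inflated. They are planned for each of these outcomes and are unaffected by change common to both arms.

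**What to change.** 1. In the protocol's Secondary Efficacy Endpoints, remove the within-group clause as an efficacy endpoint. Keep the between-group comparison of 24-month SF36 and GAQ scores, adjusted for the baseline score. The analysis plan's list of covariates does not name that score, although it is already collected.
2. In the analysis plan's primary and secondary outcome lists, mark every within-group line as descriptive: estimates with confidence intervals, no p-values.
3. Add one sentence stating that effectiveness conclusions rest only on the randomised between-group difference, and that significance within one arm is not set against significance within the other.

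The cost is a wording change in the two documents. It needs no new data and no change to design or sample size, and leaves fewer tests to report. Baseline adjustment should also improve precision: with a common variance, the variance of the between-group estimate is multiplied by about 1 − r², which is 0.75 at an assumed r of 0.5.
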